## PRÉCIS

### Background:

- Advanced breast cancer and endometrial cancer have limited treatment options. Current treatments provide a modest improvement in progression free survival but no treatments improve survival.
- ONC201 is the founding member of a novel class of anticancer drugs called imipridones. The exact mechanism of ONC201 is unknown at this time, but preclinical data suggests that it causes global downregulation of mitochondrial genes leading to mitochondrial damage and ultimately non-apoptotic cell death.
- Preclinical studies have demonstrated that ONC201 selectively kills various cancer cells, including breast cancer cells (hormone-receptor positive cell lines, HER2+ cell line as well as triple negative breast cancer cell lines) and endometrial cancer cells, while having little effect on normal cells.
- An on-going phase I study of ONC201 has demonstrated clinical benefit in some solid tumors, including endometrial cancer.

### Objectives:

- Cohort 1: To determine the progression free survival (PFS) at 8 months of ONC201 in metastatic hormone receptor positive breast cancer (HR+BC)
- Cohort 2: To determine the overall response rate (ORR) of ONC201 in metastatic triple negative breast cancer (TNBC)
- Cohort 3: To determine the ORR of ONC201 in advanced endometrial cancer (EC)

### Eligibility:

#### Selected Inclusion Criteria

- Histologically confirmed metastatic breast cancer or endometrial cancer with appropriate IHC testing and confirmation of HER2 non-amplification required for the breast cancer cohorts (cohorts 1 and 2)
- Age 18 years or older
- Female and male breast cancer patients are eligible for the breast cancer cohorts
- ECOG 0 or 1
- Measurable metastatic disease with  $\geq 1$  biopsiable lesion with willingness to undergo a biopsy
- Cohort 1 (HR+BC) requires prior treatment with  $\geq 2$  lines of hormonal treatment. No prior treatment required for cohorts 2/3 (TNBC and EC).
- Adequate hematopoietic, hepatic and renal function

#### Selected Exclusion Criteria

- Patients who have received chemotherapy in the previous 3 weeks (6 weeks for nitrosoureas or mitomycin); other investigational agents within 3 weeks or a PD1/PDL1 agent within 4 weeks prior to first dose of study treatment.

*Abbreviated Title: ONC201 in advanced cancers*

*Version Date: 06/17/2020*

- Radiotherapy  $\leq$  4 weeks before first dose of study treatment
- Symptomatic CNS metastases. Asymptomatic or brain metastases treated  $>$  4 weeks from first dose of study treatment are allowed.
- History of invasive malignancy  $\leq$  3 years
- Known history of cardiac arrhythmias including uncontrolled atrial fibrillation, tachyarrhythmias or bradycardia.
- History of CHF, or MI or stroke in the previous 3 months will be excluded.
- Started denosumab or bisphosphonate therapy within 28 days prior to Cycle 1 Day 1
- HIV, Hepatitis B, or Hepatitis C infection

**Design:**

[figure not shown]
- This is a phase II single arm study of ONC201 divided in three cohorts, each cohort with a different type of metastatic, advanced disease:
  - Cohort 1: HR+ breast cancer (male and female)
  - Cohort 2: Triple negative breast cancer (male and female)
  - Cohort 3: Endometrial cancer (female only)
- All patients will receive ONC201 at the recommended phase 2 dose (RP2D) of 625mg by mouth every 7 days with each cycle being 28 days long. Patients will receive ONC201 as long as they derive clinical benefit or toxicity becomes impeditive
- Patients will be evaluated for toxicity every 4 weeks by CTCAE v5.0 and for response every two cycles (8 weeks) by RECIST 1.1.

*Abbreviated Title: ONC201 in advanced cancers*

*Version Date: 06/17/2020*

## STUDY SCHEMA

### Study Schema Figure

\*See [Table 1](#) for dose reductions

Table 1: ONC201 Dose Reduction Schedule

Dose Level (DL)	ONC201 (by mouth)
1 (Starting Dose)	625mg every 7 days
-1	500mg every 7 days
-2	375mg every 7 days
-3	250mg every 7 days

## 1 INTRODUCTION

### 1.1 STUDY OBJECTIVES

#### 1.1.1 **Primary Objective**

- **Cohort 1 HR+BC** - To determine the progression free survival at 8 months (PFS by RECIST) of ONC201 in patients with refractory, metastatic hormone receptor positive breast cancer
- **Cohort 2 TNBC** - To determine the overall response rate (ORR; CR + PR by RECIST) of ONC201 in patients with metastatic triple negative breast cancer
- **Cohort 3 Endometrial Cancer** - To determine the ORR of ONC201 in patients with advanced or metastatic endometrial cancer

#### 1.1.2 **Secondary Objectives**

- **Cohort 1 HR+BC** – Safety, ORR, clinical benefit rate (CBR; CR + PR + SD by RECIST)
- **Cohort 2 TNBC** – Safety, CBR, PFS
- **Cohort 3 Endometrial Cancer** – Safety, CBR, PFS

#### 1.1.3 **Exploratory Studies:**

The primary goal of the exploratory studies is to identify potential predictive biomarkers of response as well as additional evidence of the mechanism of action of and resistance to ONC201. These will be performed in an exploratory fashion on select patients if there are adequate samples for analysis.

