## 5 BIOSPECIMEN COLLECTION

### 5.1 CORRELATIVE STUDIES FOR RESEARCH/PHARMACOKINETIC STUDIES

The primary goal of the correlative studies is to identify potential predictive biomarkers as well as additional evidence of the mechanism of action of and resistance to ONC201. Other correlative study aims include investigation of proof-of-concept biomarkers. These will be

*Abbreviated Title: ONC201 in advanced cancers*

*Version Date: 06/17/2020*

performed in an exploratory fashion on select patients if there are adequate samples for analysis. (**Table 4**; **Table 5**)

While the exact mechanism of ONC201 is unclear at this time, preclinical data as well as the phase I data have identified multiple potential mechanisms of action. As mentioned above, ONC201 is thought to have both TRAIL-dependent and TRAIL-independent mechanisms of killing. ONC201 has been identified as a selective antagonist of DRD2 that activates the integrated stress response in tumor cells leading to TRAIL activation. Serum prolactin will be evaluated as a surrogate marker for target engagement, which is induced by DRD2 antagonism in the pituitary gland (34). In the solid tumor phase I study, prolactin was found to increase in patients taking ONC201 and was loosely associated with response in the small trial. However, there is no evidence that DRD2 is present on tumors. In addition to serum prolactin levels, we will also evaluate select biopsy samples for the presence of DRD2.

ONC201 has shown TRAIL-dependent apoptosis as well as caspase-independent, DR4/5-independent, TRAIL-independent induction of the integrated stress response through inhibition of mitochondrial respiration. Due to these conflicting mechanisms, we will evaluate select tissue biopsy samples for markers of apoptosis including cleaved caspase-3, cleaved poly(ADP ribose) polymerase (PARP), cleaved terminal deoxynucleotidyl transferase dUPT nick end labeling (TUNEL), ATF4 expression, CHOP expression, phospho-AMPK levels, annexin-V, TRAIL receptor and TRAIL expression. We will also evaluate markers of apoptosis in the serum including TRAIL expression, M30 assays, and M65 assays. We also plan to evaluate serum cytokine levels including IL6, L24, IL32, IL1RAP, which were found to be increased after ONC201 administration on RNAseq.

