**Table 4: Correlative Studies\***

PMBC	Plasma/Whole Blood	Archived Tissue Samples	Tumor and/or Effusion Cells
Immune phenotyping Dendritic cell maturation	TRAIL levels Serum M30 assay Serum M65 assay Cytokines Circulating Tumor Cells Cell free DNA Cell free Mitochondrial DNA	Whole exome sequencing RNASeq Markers of Apoptosis TRAIL expression TRAIL receptor expression Dopamine Receptor D2	Whole exome sequencing RNASeq Dopamine Receptor D2 Electron Microscopy

\* Correlative studies will include but are not limited to the studies listed above. Correlative studies will be performed if adequate samples are collected and on select patients.

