#### **10.4.9 Exploratory Analyses**

Blood samples at baseline and Day 1 of each subsequent cycle, as well as biopsy specimens at baseline and cycle 2 will yield a set of biomarkers, such as markers of apoptosis, indications of mitochondrial damage and immune subsets. The difference of the values at cycle 1 vs. baseline and cycle 2 vs. baseline will be determined, and these differences will be used as a covariate for analysis of PFS in each cohort to see if the level of change in biomarkers may be associated with PFS. These analyses will be done in an exploratory fashion using Kaplan-Meier curves and log rank tests. The changes in the biomarkers will also be compared between responders and non-responders in the three cohorts using an exact form of a Wilcoxon rank sum test. All of these explorations will be done only if adequate patient data are available. Results will be presented without adjustment for multiple comparisons.

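### Predictive biomarkers come first among the exploratory goals, but section 10.4.9 analyses only changes from baseline and gives no test of pre-treatment marker levels against response or PFS

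*Combined protocol and SAP*

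**What the plan says.** **Goal.** Section 1.1.3: "The primary goal of the exploratory studies is to identify potential predictive biomarkers of response". Section 5.1: "The primary goal of the correlative studies is to identify potential predictive biomarkers as well as additional evidence of the mechanism of action". Both sentences also name mechanism and resistance, and both sections limit the work to selected patients with enough material.

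**Material collected before treatment.** Section 5.3.1 makes a pre-dose biopsy mandatory, section 5.4.1 takes pre-dose blood on cycle 1 day 1, and Table 4 gives the assays for archived tissue as "Whole exome sequencing RNASeq Markers of Apoptosis TRAIL expression TRAIL receptor expression Dopamine Receptor D2".

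**Analysis.** Section 10.4.9 defines the quantity to be analysed: "The difference of the values at cycle 1 vs. baseline and cycle 2 vs. baseline will be determined". For PFS, "these differences will be used as a covariate for analysis of PFS in each cohort", using Kaplan-Meier curves and log-rank tests. For response, "The changes in the biomarkers will also be compared between responders and non-responders in the three cohorts", by an exact Wilcoxon rank sum test. Results are exploratory and unadjusted for multiplicity. Section 10.4.7 plans no subgroup analyses.

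**The concern.** A marker meant to predict who will respond has to be readable before treatment starts. A change measured at cycle 2 is not, and it may be a consequence of response rather than a predictor of it.

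If 10.4.9 is followed as written, the pre-treatment values of DRD2, death receptors, TRAIL, RNAseq, exome data and immune subsets are never tested against outcome. On-treatment changes would be reported in their place under a goal labelled predictive. Patients undergo mandatory biopsies partly for that goal. If baseline analyses are then done anyway, they will have been chosen after the data are seen, in cohorts of 24 to 29.

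**Working it through.** The documents give no power, alpha or sample size for the exploratory analyses, so there is no figure to reproduce. The check is mainly a comparison of texts, with an illustration of size.

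**1. Every place that links a marker to an outcome**

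| Place | Marker quantity | Outcome | Method stated |
|---|---|---|---|
| 10.4.9, first analysis | Change from baseline | PFS | Kaplan-Meier, log-rank |
| 10.4.9, second analysis | Change from baseline | Response | Exact Wilcoxon |
| 5.1, CTC enumeration | Levels at baseline and after therapy | Response or survival | None |
| 5.6.2, sample storage | Genotype | Variables that include date of death | None |

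In 10.4.9, 0 of 2 analyses use a baseline level. Outside it there is one explicit plan (CTCs) and one loose statement (genotype), both without a method.

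**2. Archived tissue**

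Table 4 lists six archived-tissue assays. An archived block gives one pre-treatment time point, so that result on its own has no difference and cannot enter 10.4.9. The same markers are largely planned on fresh biopsies too. Table 5 has DRD2, death receptors, exome sequencing and RNAseq at cycle 1 day 1 pre-dose and at cycle 2 day 2. Section 5.1 plans apoptosis markers, TRAIL and TRAIL receptor on selected biopsy samples. Differences can therefore exist for most of them, but again only the difference would be tested.

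**3. Illustration for PFS, cohort 1**

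From section 10.2: 24 patients, a 4-month median PFS, about 2 years of accrual and at least 1 year of further follow-up, taken here as censoring uniform on 12 to 36 months. Assumed, with no source in the documents: exponential PFS, a normal baseline marker with hazard ratio 2.0 or 1.5 per SD, no separate effect of change, a median split for the log-rank test, and two-sided 5%. There were 1,500 simulated trials per setting, so the standard error is at most √(0.5 × 0.5 / 1500) = 1.3 percentage points.

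The result for change depends on its correlation with baseline. If baseline and follow-up have equal variance and correlation r, then corr(baseline, change) = −√((1 − r)/2). This gives −0.39 for r = 0.7, −0.50 for r = 0.5 and −0.63 for r = 0.2.

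| Analysis | HR 2.0 per SD | HR 1.5 per SD |
|---|---|---|
| Log-rank, change, independent of baseline | 5.5% | 5.3% |
| Log-rank, change, r = 0.7 | about 11% | about 11% |
| Log-rank, change, r = 0.5 | about 17% | about 11% |
| Log-rank, change, r = 0.2 | about 25% | about 14% |
| Log-rank, baseline (like for like) | 59.2% | 28.9% |
| Cox, baseline, continuous | 81.4% | 42.3% |

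The first row is the false-positive rate and follows from the independence assumption. The step from 59.2% to 81.4% comes from not splitting the marker, so the fair comparison with the change rows is 59.2%.

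**4. Illustration for response**

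Assumed: exact Wilcoxon test on baseline values, two-sided 5%, normal markers with equal SD. The 11 of 29 and 4 of 25 responders are examples in section 10.2; 6 of 25 is close to the 25% target rate there.

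| Responders vs non-responders | Power at 1.0 SD | Difference giving over 80% power |
|---|---|---|
| 11 vs 18 (TNBC) | 69% | 1.2 SD (83%) |
| 6 vs 19 (endometrial) | 49% | 1.5 SD (82%) |
| 4 vs 21 (endometrial) | 39% | 1.8 SD (82%) |

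A baseline comparison is feasible with the planned numbers, but it would detect only large differences.

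**The case against.** The work is labelled exploratory, the goal is only *potential* predictive biomarkers, and the same sentences also name mechanism and resistance. Change scores are a direct way to study mechanism. No endpoint, stopping rule or sample size rests on 10.4.9. A single arm cannot separate a predictive marker from a prognostic one, so even a baseline analysis does not fully deliver the goal. All of this stands, and it limits how much weight the point can carry.

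Three stronger readings are tempting, and the documents do not support them.

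- *That no baseline value is ever related to outcome.* Section 5.1 plans exactly that for CTCs, and 5.6.2 hints at it for genotype.
- *That the predictive goal cannot be met.* The pre-dose samples are collected, so the analysis is unspecified rather than impossible.
- *That the archived-tissue assays are all unusable.* Most of those markers are also planned on paired fresh biopsies.

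A reader might also set 81% against 5% as the size of the loss. That contrast assumes that change is independent of baseline, and it compares a continuous Cox model with a median-split log-rank test.

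What the objection does not answer is that, for nearly all listed markers, no stated method tests the pre-treatment level against response or PFS.

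**Conclusion.** The mismatch is real but limited. Section 10.4.9 specifies change-from-baseline analyses only. Apart from the CTC correlation in 5.1 and the genotype remark in 5.6.2, no analysis relates a pre-treatment level to response or PFS. The written plan addresses mechanism and leaves the first-named aim without an analysis.

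That conclusion rests on the text alone. The simulated percentages show only that, if the information lies in the baseline level, an analysis of change would recover little of it. They depend on assumed hazard ratios and on the assumed relation of change to baseline, and they say nothing against change scores as pharmacodynamic measures. This is worth correcting before analysis because the correction is cheap. It does not affect the trial's primary or secondary conclusions.

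**What to change.** Add to section 10.4.9, in substance:

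*For each marker with a pre-treatment value (archived tissue, pre-dose biopsy or pre-dose blood), the baseline level will be related to PFS by Cox regression as a continuous covariate, with a 95% confidence interval, and compared between responders and non-responders by an exact Wilcoxon test, using all patients with an adequate baseline sample.*

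Keep the change analyses and label them pharmacodynamic. Apply the same stated method to the CTC correlation in 5.1. Word any result as *associated with outcome on ONC201*, since there is no comparator.

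No new samples or visits are needed, and patients with only a first sample still contribute. The cost is SAP wording, some extra analyses, and more unadjusted exploratory comparisons in cohorts of 24 to 29. Reporting how many markers were tested would let readers judge that cost: at a 5% level, about one in 20 null markers will appear associated by chance.

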### 1.2 BACKGROUND AND RATIONALE

This is a phase II study of ONC201 for the treatment of metastatic hormone receptor positive breast cancer, metastatic triple negative breast cancer, and endometrial cancer. At this time, there is no clear benefit to the combination of ONC201 plus anti-HER2 therapies. However, we plan to develop preclinical data for ONC201 in combination with HER2 targeted drugs (*e.g.*, trastuzumab, trastuzumab emtansine, and lapatinib) and we anticipate initiating a Phase I run-in study at a later date.

#### 1.2.1 **Current Standards of Care for Recurrent/Refractory Invasive Breast Cancer**

Invasive breast cancer remains the most common malignancy in women in the United States with an annual incidence of 123.1 cases per 100,000 women (5). Treatment of invasive breast cancer involves local control with surgery and/or radiation where appropriate, as well as systemic control with endocrine therapy, HER2 targeted therapy, and chemotherapy. Despite advances in early detection and effective treatments, breast cancer is the second most common cause of US cancer deaths in women with an annual rate of 21.9 deaths per 100,000 women (5). It is estimated that in 2017, there will be 252,710 new cases of breast cancer with 40,610 deaths (6).

### 1.2.1.1 Hormone Receptor Positive Breast Cancer

Hormone receptor positive breast cancer (HR+BC) accounts for approximately 75% of all breast cancers and is defined by immunohistochemical (IHC) staining of at least  $\geq 1\%$  of tumor cells with estrogen receptors and/or  $\geq 1\%$  with progesterone receptors. Despite optimal treatment, up to 30% of women with node-negative breast cancer recur after their initial diagnosis. While the risk is greatest within the first two years of diagnosis, women with HR+BC have an increased risk for recurrence up to 25 years after diagnosis (7, 8). Recurrence can be loco-regional or metastatic. Once metastatic, there are limited effective treatments and overall prognosis is poor.

Generally, patients with metastatic or recurred disease are first treated with endocrine therapy alone (e.g. tamoxifen, aromatase inhibitors, or fulvestrant) or, more recently, endocrine therapy in combination with CDK 4/6 inhibitors or mTOR inhibitors (9). However, once the cancer is determined to be hormone refractory, chemotherapy is the next treatment option.

Combination chemotherapy regimens have higher response rates and longer progression free survival (PFS), but with higher toxicity profiles and no added survival benefit when compared to single agent chemotherapy regimens (10). Therefore, the use of sequential single agents is the favored regimen once the cancer is refractory to endocrine therapy. Preferred single agents, like paclitaxel or capecitabine, carry a PFS of 5.7 to 8.0 months (11, 12). Both endocrine therapy and chemotherapy in this setting have been shown to have palliative benefit but no curative therapies exist.

### 1.2.1.2 Triple Negative Breast Cancer

Triple-negative breast cancer (TNBC) accounts for 10-20% of all breast cancers, and is defined by the absence of estrogen and progesterone receptors (ER, PR) and the absence of HER2 amplification or over-expression (13). Thus, patients with TNBC do not benefit from known targeted therapies to ER or HER2 (14). Standard therapy for metastatic TNBC is single agent chemotherapy and, in metastatic patients, ORRs are around 30-35%, with median PFS 4.5-6 months, and median OS around 12 months (15). Clearly, new approaches to the treatment of TNBC are needed to improve outcomes.

## 1.2.2 Current Standards of Care for Endometrial Cancer

Endometrial adenocarcinoma is the most common malignancy of the female genital tract with an estimated 61,380 new cases and 10,920 deaths in 2017 (6). While endometrial cancer is often found in early stages due to irregular vaginal bleeding in a predominantly postmenopausal population, there has been a recent increase in cancer-related mortality (16). This is suspected to be due to an increase in advanced-stage cancers, high risk histologies (e.g., serous carcinomas or clear cell carcinomas) and patients being diagnosed at an older age (16). In addition, there is an increased risk of endometrial cancer in patients with Lynch Syndrome (17).

Multi-agent chemotherapy regimens are preferred in the relapsed or advanced/metastatic setting. Current first line chemotherapy regimens have response rates ranging from 21% to 81%. These

*Abbreviated Title: ONC201 in advanced cancers*

*Version Date: 06/17/2020*

responses are of short duration with median progression free survival of approximately one year (18, 19). Due to a relatively low toxicity profile and multiple studies demonstrating improved survival, carboplatin and paclitaxel is the preferred regimen for advanced/metastatic or recurrent endometrial cancer with response rates of 40 to 62% and overall survival from 13 to 29 months (20). If a multi-drug regimen cannot be tolerated, single agent treatment with paclitaxel (most active), cisplatin, carboplatin, doxorubicin, liposomal doxorubicin, topotecan, or docetaxel can be used. However, response rates with single agents are lower (first-line treatment response rate 21% to 36%; second line treatment response rates 4% to 27%) (21). None of these therapies are curative and second line therapies have not been shown to improve survival (21). New therapies are needed to improve outcomes in patients with advanced stage endometrial cancers.

### **1.2.3 Development of ONC201**

#### **1.2.3.1 Preclinical Development of ONC201**

ONC201 (also known as TIC10 and NSC350625) is the founding member of a novel class of anti-cancer compounds called imipridones (22). It is an orally active small molecule that was initially identified by a screen for small molecules that could induce tumor necrosis factor (TNF) –related apoptosis-inducing ligand (TRAIL) on colon cancer cells, and activate the TRAIL death receptors on those cells inducing an autocrine apoptotic death.

**Abbreviated Title:** *ONC201 in advanced cancers*

**Version Date:** 06/17/2020

TRAIL is a type II transmembrane protein that is expressed in various tissues and cells including the surface of Natural Killer (NK) and T cells, macrophages and dendritic cells (23, 24). On immune cells, the expression of TRAIL plays a role in immune surveillance in the prevention of tumors and metastasis (25). Humans have five distinct TRAIL receptors (26, 27). Death receptor 4 (DR4) and DR5 contain intracellular death domains and are capable of signaling apoptosis. There are two membrane-bound decoy receptors called DcR1 and DcR2 which lack a functional death domain and while unable to activate apoptosis, are able to inhibit TRAIL signaling. Osteoprotegerin is the fifth TRAIL-binding receptor which also functions as a decoy/inhibitor by sequestering TRAIL extracellularly. TRAIL is attractive as an anti-tumor agent because of its capability to induce apoptosis in cancer cells by activating DR4 and DR5 with little toxicity against normal cells (23, 28). In our preclinical work, we have shown that TRAIL receptor agonists are most active against triple negative breast cancer and in particular those with mesenchymal features (29, 30).

Despite their robust cell killing of tumor cells *in vitro* and in animal models *in vivo*, efficacy of TRAIL receptor agonists has been limited in clinical trials. The limited activity is thought to be due to lack of reliable predictive biomarkers of sensitivity and drug properties that limit efficacy

such as short serum half-life, stability, and bio-distribution (25, 28, 31). There is a need to find alternative approaches to activating the DR pathways. ONC201 induces sustained up-regulation of TRAIL in tumor cell lines, which activates DR through autocrine and paracrine mechanisms.

Several alternative mechanisms have also been proposed for the anticancer activity of ONC201, including inhibition of the dopamine receptor D2 (DRD2), and activation of an atypical integrated stress response in tumor cells (32, 33).

[figure not shown]
[figure not shown]

Figure 1: Structure and mechanism of action of ONC201. In the TRAIL-dependent pathway, ONC201 inhibits both AKT and MEK, resulting in the dephosphorylation of the transcription factor FOXO3a. This enables its translocation from the cytoplasm into the nucleus where it binds to the TRAIL promoter and upregulates gene transcription of TRAIL. Apoptosis occurs through activation of TRAIL-DR receptors. In the TRAIL-independent pathway, ONC201 induces a stress response through an unknown mechanism which differs between solid tumors and hematologic malignancies. The mechanism of ONC201 appears to be different in breast cancer cell lines, where ONC201 demonstrates caspase-independent, DR4/5 independent mechanisms distinct from TRAIL-induced apoptosis. Instead it induces mitochondrial dysfunction and ATP depletion. *Image adapted from Greer and [name], 2016: (3).*

*Abbreviated Title: ONC201 in advanced cancers*

*Version Date: 06/17/2020*

**Figure 2:** IC50 for breast cancer cell lines treated with ONC201. Cells were treated with a dose curve of ONC201 for 5 days and viability measured by MTS assay. The data represent the mean IC50 for each cell line (Greer and [name], unpublished observations).

ONC201 has been extensively investigated in the [name] lab as a promising means to kill tumor cells. Rather than a simple induction of TRAIL and induction or DR receptor-dependent apoptosis, both the [name] lab and independent labs have shown that ONC201 has both TRAIL-dependent and TRAIL-independent pathways of inducing death (**Figure 1**— two right sided pathways).

We have investigated the mechanism by which ONC201 kills breast cancer cells. Unexpectedly, ONC201 did not induce caspase 3 or PARP cleavage, and its toxicity was not inhibited by Z-VAD-FMK, nor by siRNA

knockdown of DR4 or DR5. By contrast GST-TRAIL induced caspase 3 and PARP cleavage and GST-TRAIL-induced cell death was inhibited by Z-VAD-FMK and by siRNA knockdown of DR5. Live cell imaging revealed ONC201 induces cell membrane ballooning followed by rupture consistent with necrosis, whereas GST-TRAIL induced classic apoptosis morphology. Together these results suggest that ONC201 kills breast cancer cells via a caspase-independent, DR4/5-independent mechanism distinct from TRAIL-induced apoptosis. ONC201 does induce ATF4 and CHOP, consistent with the recently published observations of another group (32, 33).

Further mechanistic studies in the [name] lab showed that ONC201 induced transcriptional down regulation of multiple nuclear encoded mitochondrial genes, resulting in decreased mitochondrial oxidative phosphorylation and ATP production (**Figure 1**— right pathway). Our data suggest that in addition to the published mechanisms, ONC201 can kill breast cancer cells by a novel mechanism involving inhibition of mitochondrial respiration. In breast cancer cells this appears to be the dominant mechanism. One of the reasons for conducting this trial in the Intramural program is to validate and expand our understanding of ONC201's mechanism of action in the human. Such data will translate back to the bench, enabling the development of combination therapies and plans for overcoming resistance.

[figure not shown]
We have tested ONC201 across a range of breast cancer cell lines and have found that all subtypes are inhibited by ONC201, and the IC50s for the cell lines range from 0.8-5 $\mu$ M (**Figure 2**). This is within the achievable concentrations that were seen in pharmacokinetic studies from phase I studies (2).

**Abbreviated Title:** *ONC201 in advanced cancers*

**Version Date:** 06/17/2020

ONC201 has been evaluated as a therapeutic agent *in vitro* as well as *in vivo* in various cell lines. Single-dose experiments in HCT116 wild-type (human colon cancer) xenograft-bearing mice corroborated the antitumor activity of ONC201 (TIC10) (Figure 3). *In vivo* experiments have shown promising anti-tumor effects in 12 subcutaneous xenografts (including triple negative breast cancer, non-small cell lung cancer, hepatocellular carcinoma, glioblastoma, colon cancer and head and neck squamous cell carcinoma), one orthotopic xenograft

(glioblastoma) and one transgenic (lymphoma) model. [name] group has demonstrated that ONC201 inhibits xenografts of the triple negative breast cancer cell line MDA-MB-231 (1).

**Figure 3:** Bioluminescence imaging of luciferase-expressing HCT116 p53-/- xenografts that received a single intraperitoneal injection of ONC201 (TIC10) or vehicle (n = 6). Image from *Allen et al, 2013 (1)*.

